8.1 Definitions

Adverse event

An adverse event for medicines is also referred to as an adverse experience, any untoward medical occurrence in a patient or clinical investigation participant administered a pharmaceutical product and which does not necessarily have a causal relationship with this treatment. An adverse event can therefore be any unfavourable and unintended sign, symptom, or disease temporally associated with the use of a medicinal (investigational) product, whether or not related to the medicinal (investigational) product.

Devices Events

An adverse event for devices is any undesirable clinical occurrence in a participant whether it is considered to be device related or not, that includes a clinical sign, symptom or condition and/or an observation of an unintended technical performance or performance outcome of the device.

In relation to devices any adverse medical occurrences include: death and or a serious deterioration in health of a patient user or other. This would include:

- a life threatening illness or injury;
- a permanent impairment of body function or permanent damage to a body structure
- a condition requiring hospitalisation or increased length of existing hospitalisation
- a condition requiring unnecessary medical or surgical intervention or
- death or a serious deterioration in health had suitable action or intervention not taken place
- a malfunction of a device such that it has to be modified or temporarily/permanently taken out of service; or a factor (deterioration in characteristics or performance) found on examination of the device

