8.3 Serious Adverse Event Reporting

8.3.1 SAEs

Serious adverse events will be recorded in the study data, and site-specific HREC reporting for incident and risk management will be followed.

Serious adverse event (SAE):

An unforeseen medical event that occurs in the course of clinical research that:

- results in participant death
- is life-threatening to the participant
- requires the inpatient hospitalisation or prolongation of existing hospitalisation and leads to the participant having a persistent or significant disability/incapacity.

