9.4 Interim Analyses

Interim review of recruitment will occur at the 6 month period, and interim analysis of preliminary data will occur at the 1 year mark. Sample size estimates will be reassessed given actual rates of enrolment after the 6 month period to ensure that the a priori sample size calculated is realistic, and the trial may be extended to allow for adequate patient recruitment. The trial will not be stopped for superiority reasons unless the adverse event rate and safety of the product is determined to be significant. Significance of the primary outcome will be assessed with an interim stopping level of $p=0.001$ using the Peto approach. (23)

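### Section 8.3.1 joins hospitalisation and lasting disability with 'and', so neither alone makes an event an SAE, which does not fit the device-event list in 8.1

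*Combined protocol and SAP*

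**What the plan says.** Section 8.3.1 SAEs defines a serious adverse event as an unforeseen medical event that meets one of three bullets. The first two are death and threat to life. The third is that the event "requires the inpatient hospitalisation or prolongation of existing hospitalisation and leads to the participant having a persistent or significant disability/incapacity".

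The same section says what the label sets in motion: "Serious adverse events will be recorded in the study data, and site-specific HREC reporting for incident and risk management will be followed". Section 8.3.2 applies the same recording and reporting to SUSARs and gives no definition of serious of its own.

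Section 8.1 Definitions, under its device heading, opens a second list with "In relation to devices any adverse medical occurrences include: death and or a serious deterioration in health of a patient user or other". Two of its bullets are "a permanent impairment of body function or permanent damage to a body structure" and "a condition requiring hospitalisation or increased length of existing hospitalisation". Neither is conditional on the other.

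**The concern.** Hospitalisation (or its prolongation) and lasting disability look like two separate criteria that have been run together. Joined by 'and' in one bullet, they become a single criterion that needs both.

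This matters because of the events the trial can expect. The background (2.1) names longer stay, readmission and re-operation among the possible consequences of wound complications after transplant. An event of that kind that leaves no lasting disability, and is neither fatal nor life-threatening, falls outside the SAE class as 8.3.1 is worded. At stake are its classification as serious and the ethics-committee reporting that follows. Staff at three sites apply this text, and those who read 8.1 and those who read 8.3.1 could grade the same event differently.

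**Working it through.** No arithmetic applies: the point turns on the wording of a definition, and the plan states no figure for SAEs. The check is to set the two lists side by side and classify the same events under each.

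**Inputs.** The three bullets of 8.3.1, and the hospitalisation and impairment bullets of 8.1 with their lead-in.

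**Reading 8.3.1.** Death and threat to life each have a bullet of their own. The third bullet has one subject and two verbs joined by 'and'. For an event that is neither fatal nor life-threatening, the literal rule is therefore: SAE = (hospitalisation or prolongation) AND (persistent or significant disability/incapacity).

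**Comparison, for unforeseen events that are neither fatal nor life-threatening:**

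| Event | SAE under 8.3.1? | In the 8.1 device list? |
|---|---|---|
| (a) Readmission or prolonged stay, no lasting disability | No | Yes, hospitalisation bullet |
| (b) Permanent impairment, no hospitalisation | No | Yes, impairment bullet |
| (c) Both together | Yes | Yes |

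The lists part on (a) and (b). The match in (b) is looser, because 8.1 speaks of permanent impairment or damage and 8.3.1 of persistent or significant disability.

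**Is it corrected elsewhere?** Nothing in the available text says that either feature alone makes an event an SAE. The schedule in section 6 lists adverse event and SAE assessment at Days 7, 14, 30 and 90 but gives no criteria.

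**What depends on the label?**

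- *Ethics-committee reporting of SAEs (8.3.1):* depends on it directly.
- *SUSARs (8.3.2):* depend on it through the word serious, for which 8.3.1 has the only definition labelled as such.
- *Capture of the events:* does not depend on it. Section 8.2 documents all adverse events in the database. Section 4.2 records re-presentation with a wound complication, re-operation and further intervention. Section 4.6 makes reoperation, length of stay and clinical adverse events secondary outcomes. The Appendix B form records a stay beyond 14 days and readmission.
- *Planned analyses (9.3):* no comparison of SAEs between arms is specified.
- *Interim rule (9.4):* "The trial will not be stopped for superiority reasons unless the adverse event rate and safety of the product is determined to be significant". It names the adverse event rate and product safety, not SAEs.

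**The case against.** **It is a drafting slip.** The verbs run in parallel (results in, is, requires, leads to), so the 'and' may simply have introduced a last list item whose line break was lost, possibly even when the PDF was read. That is plausible but cannot be shown from the text. Unless the source page shows a separate bullet, sites are given a definition that says both.

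**Section 8.1 is not an SAE definition.** This is correct. The list concerns device events, also covers malfunction, and words its impairment item differently. An event could be on it without being an SAE and without strict contradiction. But its lead-in speaks of death or serious deterioration in health, which makes it a seriousness list in substance. The inconsistency stands, as one between two lists rather than between two definitions with the same label.

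**The events are recorded anyway.** This is also correct, and it limits the point. The data are not lost. What is lost is the serious label and what follows from it. Even there, 8.3.1 defers to site-specific reporting and section 8 to a national position statement. Neither is reproduced in the protocol, so it cannot be shown that these events would go unreported by every route.

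**Stronger readings a reader might infer.** Three are tempting, and the documents do not support them:

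- *A biased comparison of serious events between arms.* Section 9.3 plans no such comparison. Only a descriptive table by seriousness, if one were made, would be affected.
- *A weakened one-year interim review.* Section 9.4 refers to the adverse event rate, which 8.2 feeds whatever the SAE label.
- *A number of missed SAEs.* The planning rates give 0.15 × 250 + 0.07 × 250 = 37.5 + 17.5 = 55 patients with a wound complication. If 20% to 50% of them were readmitted or stayed longer, that would be 11 to about 28 patients. The 20% to 50% is an assumption with no basis in the documents. The figure also ignores that 8.3.1 covers only unforeseen events. Wound complications are the primary outcome, and 2.1 calls them arguably the commonest surgical complication after transplant, so many might be excluded as foreseen even with the bullet split.

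**Conclusion.** The definition is wrong as written, and the point is of moderate importance. Taken literally, 8.3.1 leaves two kinds of event outside the SAE class: hospitalisation or prolonged stay without lasting disability, and lasting disability without hospitalisation. The 8.1 device list carries both features as stand-alone items. The consequence is confined to the serious label, the ethics-committee reporting tied to it, and the serious element of SUSARs.

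No count of affected events can be derived from the documents. The primary analysis, sample size, alpha and interim rule are not shown to be affected. The conclusion rests on the literal reading of the bullet and on there being no correcting text elsewhere. Confidence is high in the reading, and lower in how often it would change what a site reports.

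**What to change.** 1. Split the third bullet of 8.3.1 into two stand-alone criteria: inpatient hospitalisation or its prolongation; and persistent or significant disability or incapacity.
2. Reconcile 8.3.1 with the device list in 8.1. Either state that the 8.1 list is the seriousness list for device events or cross-refer to a single list, and settle the difference between permanent impairment and persistent or significant disability.
3. State whether the word unforeseen in the 8.3.1 lead-in is meant to exclude expected wound complications. Without this, splitting the bullet may change little for the events the trial is most likely to see.
4. Check that the SAE form in the study database uses the corrected list. Appendix C, which 8.2 cites for adverse events, is not in the text available for this review, so whether the form carries the merged wording is unknown.

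The cost is a wording amendment submitted to the ethics committee, a form change if the check shows one is needed, and somewhat more SAE reports. No analysis or sample-size change follows.

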8.3.2 SUSARs

Suspected Unexpected Serious Adverse Reactions (SUSAR) will be recorded in the study data, and site-specific HREC reporting for incident and risk management will be followed.

9 STATISTICAL METHODS

9.1 Sample Size Estimation

Wound infection rate have been estimated between 5 and 30% based on a current literature, including a systematic review and meta-analysis.(3)(10) Weighting the participating site's preliminary audit data by expected enrolment rates, the average wound complication rate was estimated to be 15%. NPWT has been suggested to offer an approximate 46% reduction in wound infection rates for abdominal incisions (3)(10).

Based on a two-sided type one error of $\alpha = 0.05$ and a type two error of $\beta = 0.2$ (corresponding to a power of 80%) a total sample size of 239 patients per group (478 in total) is needed to evaluate primary

endpoints, which was calculated using the power formula for a chi-square test without Yates' continuity correction due to the large sample size and binary dependent variable (22). Accounting for potential loss to follow up, which is estimated to be minimal, as every patient receiving a kidney transplant is planned to follow up every day for 30 days postoperatively, the sample size has been rounded up to 250 per arm (500 total). Missing data from patients who fail to have endpoints recorded will be treated on an intention to treat basis with last observation carried forward.

Estimated mean wound complication rate in control arm across 3 sites : 15%

Site 1 : 5-10% (60 transplants per year, audit data demonstrates 5% dehiscence rate)

Site 2 : 8-15% (90 transplants per year, audit data demonstrates 8% infection rate)

Site 3 : 18-25% (100 transplants per year, audit data demonstrates 18% dehiscence rate)

Conservative estimate of treatment effect: ~50% reduction in all wound complications with closed incision NPWT over lower abdominal/groin wounds (Rutherford Morrison) in high risk population.

Estimated complication rate for Prevena arm (intervention) = 7%

Dichotomous Endpoint, Two Independent Sample Study

Sample Size	
Group 1	239
Group 2	239
Total	478

Study Parameters	
Incidence, group 1	15%
Incidence, group 2	7%
Alpha	0.05
Beta	0.2
Power	0.8

$$N_1 = \left\{ z_{1-\alpha/2} * \sqrt{\bar{p} * \bar{q} * \left(1 + \frac{1}{k}\right)} + z_{1-\beta} * \sqrt{p_1 * q_1 + \left(\frac{p_2 * q_2}{k}\right)} \right\}^2 / \Delta^2$$

$$q_1 = 1 - p_1$$

$$q_2 = 1 - p_2$$

$$\bar{p} = \frac{p_1 + k p_2}{1 + K}$$

$$\bar{q} = 1 - \bar{p}$$

$$N_1 = \left\{ 1.96 * \sqrt{0.11 * 0.89 * \left(1 + \frac{1}{1}\right)} + 0.84 * \sqrt{0.15 * 0.85 + \left(\frac{0.07 * 0.93}{1}\right)} \right\}^2 / 0.08^2$$

$$N_1 = 239$$

$$N_2 = K * N_1 = 239$$

p_1, p_2 = proportion (incidence) of groups #1 and #2
 $\Delta = |p_2 - p_1|$ = absolute difference between two proportions
 n_1 = sample size for group #1
 n_2 = sample size for group #2
 α = probability of type I error (usually 0.05)
 β = probability of type II error (usually 0.2)
 z = critical Z value for a given α or β
 K = ratio of sample size for group #2 to group #1

Kane SP. Sample Size Calculator. ClinCalc: <http://clincalc.com/stats/samplesize.aspx>. Updated July 1, 2017. Accessed August 24, 2018.

9.2 Population to be analysed

Every patient presenting for renal transplant that meets the criteria for inclusion and exclusion will be included for intention to treat analysis. Secondary analysis as per protocol will also be performed.

9.3 Statistical Analysis Plan

Statistical analysis will be pre-specified and conducted according to both principles of intention to treat and per-protocol analysis, using SPSS version 20 (IBM, Armonk, NY, USA). Each incision will be randomized to the Prevena or standard dressing group. In the case that a patient requires bilateral incisions, both incisions will be allocated to the same treatment arm and counted as a single incision. Baseline characteristics of the two groups will be recorded and compared using Student's t-test and chi-square test for continuous and discrete data respectively. The primary outcome, the proportion of wound complications, will be compared between the Prevena and standard dressing groups using a chi-square test without Yates' continuity correction with a two-sided alpha of 0.05 at the final analysis using the Peto approach to preserve the overall significance level of 0.05 (23). An absolute risk increase/reduction for wound complications will be presented for the use of Prevena, as well as the number needed to treat in order to prevent specific wound complications. Patients lost to follow-up will be used in an intention-to-treat analysis with last observation carried forward.

The secondary outcome of identification of risk factors for wound complications will be assessed by multiple logistic regression of collected variables to assess their odds ratio. To prevent overfitting with the selected sample size, variables will be stepwise selected and also assessed for multicollinearity with the significance level of the dependent variables adjusted for multiplicity. Secondary outcomes will be compared between groups using a chi-square or Fisher's test for reoperation rate and delayed graft function and t-test for continuous variables, including the pain scale and quality of life. Non-normally distributed continuous variables will be tested for and compared using the Mann-Whitney *U* test. Survival analysis will be performed for allograft survival time with subjects without events censored at the 90 day final observation. A *p* value of less than 0.05 will be considered significant for the secondary outcomes and all tests will be two-sided.

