Study Procedures	Participants will be randomised to either a Prevena (intervention arm) or standard dressing (control arm) is placed on the closed incision after renal transplantation. Monitoring will occur daily during hospitalization and up to 30 days postoperatively to review any wound complications, with subsequent assessment at 90 days.
Statistical Procedures and Analysis Plan:	Statistical analysis will be pre-specified and conducted according to both principles of intention of treat and per-protocol analysis, using SPSS version 20 (IBM, Armonk, NY, USA). The Intention to Treat (ITT) sample will be based on all enrolled subjects, and the per-protocol analysis will be based on all patients who have a dressing placed on the closed incision following renal transplant. Each incision will be randomized to the Prevena or standard dressing group. In the case that a patient requires bilateral incisions, both incisions will be allocated to the same treatment arm and counted as a single incision. Baseline characteristics of the two groups will be recorded and compared using Student's t-test and chi-square test for continuous and discrete data respectively. The primary outcome, the proportion of wound complications, will be compared between the Prevena and standard dressing groups using a chi-square test without Yates' continuity correction with a two-sided alpha of 0.05 at the final analysis using the Peto approach to preserve the overall

	
significance level of 0.05 (23). Patients lost to follow-up will be used in an intention-to-treat analysis with last observation carried forward
 
The secondary outcome of identification of risk factors for wound complications will be assessed by multiple logistic regression of collected variables to assess their odds ratio.

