4. STUDY DESIGN

4.1 Type of Study

This study is a multicentre, partially-blinded, randomised controlled trial, with site stratified block randomisation and partial blinding of outcome assessments. Patients undergoing a renal transplant will be allocated to one of two treatment arms, where either a Prevena or standard dressing is applied to the closed incision.

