4.4 Study sites

The study sites are Royal North Shore Hospital, Royal Prince Alfred Hospital and Westmead Hospital, located in Sydney, Australia. Outside the confines of this research protocol, surgeons at each site will perform the renal transplantation as per their own procedural methodology, and perioperative management will be as per site specific protocol and guidelines.

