5.4 Enrolment and Randomisation Procedures

All patients presenting for a renal transplant over a 24 month period at one of the participating sites will be eligible for enrolment in this study. Patients who sign the Participant Information Sheet and Consent Form (PISCF) and fulfil all inclusion and exclusion criteria, as well as compliance with contraindications listed in the Prevena IFU, will be considered eligible for study participation. Participants may recruited at any point prior to surgery once surgery is confirmed, ideally at the time of admission to hospital for the procedure, or if this is not possible, at the time consent is obtained for the surgery. A unique study identification number is then assigned to enrolled participant by the study investigators.

Participants who signed the PISCF but do not fulfil all inclusion and exclusion criteria, IFU related indications and contraindications, hospital standard of care tests, or who withdraw informed

consent prior to the procedure are screen failures. They will be documented on the screening and enrolment log with the screening failure reason. For the purposes of analysis, an Intention to Treat (ITT) sample will be based on all enrolled subjects, and a secondary as per-protocol analysis will be based on all patients who have the intervention of having a dressing placed on the closed incision following renal transplant.

Patient registration will occur prior to surgery on an online research database (REDCap; Vanderbilt University, Nashville, USA) hosted at Royal North Shore Hospital (19). Randomisation via REDCap will occur when the patient fulfils all intra-operative exclusion criteria and after commencement of skin closure (defined as closure to the muscle, subcutaneous tissue and skin). Randomisation will be stratified by site, with block randomisation by variable block size in a 1:1 ratio. , The surgical team, clinical staff, and patient will not be blinded to the intervention status.

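### Randomisation is stratified by site and site risks are expected to differ two- to threefold, but the primary chi-square ignores site: valid, slightly conservative, usually under 1 point of power lost

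*Combined protocol and SAP*

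**What the plan says.** Section 4.1 describes a trial "with site stratified block randomisation and partial blinding of outcome assessments". Section 5.4 adds: "Randomisation will be stratified by site, with block randomisation by variable block size in a 1:1 ratio".

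Section 9.1 gives each site's expected rate and volume. Site 1 is put at 5-10% on a volume of 60 a year (5% dehiscence at audit), and site 2 at 8-15% on a volume of 90 a year (8% infection at audit). The entry for the site with the highest expected risk reads: "Site 3 : 18-25% (100 transplants per year, audit data demonstrates 18% dehiscence rate".

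Section 4.4 says that "perioperative management will be as per site specific protocol and guidelines", so site also determines background care.

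For the analysis, the synopsis and section 9.3 use the same sentence: the primary outcome "will be compared between the Prevena and standard dressing groups using a chi-square test", uncorrected and two-sided at 0.05. Neither place brings in site, and no other section does so for the primary outcome. The only multivariable model is the stepwise logistic regression for risk factors, which is secondary. The absolute risk reduction and number needed to treat in 9.3 are also described without site. Section 9.4 tests the primary outcome at the interim against p = 0.001 and names no separate test.

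**The concern.** When arms are balanced within site, differences in risk between sites cannot contribute to the difference between arms. A pooled chi-square treats all 500 patients as one homogeneous sample, so its variance still contains the between-site part. The variance is overstated, the p-value is on average slightly too large, and some precision is lost. The more the sites differ in risk, the larger the loss.

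At stake is a little efficiency and the match between design and analysis. There is no bias and no added false-positive risk. The choice should be made in advance, because choosing between adjusted and unadjusted results after seeing the data would be open to challenge.

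**Working it through.** **Plan's own figure.** With 15% v 7%, two-sided alpha 0.05 and 80% power, the formula in 9.1 gives {1.96·√(0.11·0.89·2) + 0.84·√(0.15·0.85 + 0.07·0.93)}² / 0.08² = (0.867 + 0.369)² / 0.0064 = 238.7, so 239 per group. The plan's figure reproduces. At 250 per arm the same formula gives 81.8% power.

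**Spread between sites.** The ratio of site 3 to site 1 is 18/5 = 3.6 at the low ends, 21.5/7.5 = 2.9 at midpoints and 25/10 = 2.5 at the high ends. Pairing opposite ends gives 18/10 = 1.8 to 25/5 = 5.

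**Variance the pooled test wrongly includes.** Weights from 60, 90 and 100 transplants per year are 0.24, 0.36 and 0.40. At midpoints (7.5%, 11.5%, 21.5%) the mean rate is 0.1454.
- Pooled variance per patient: 0.1454 × 0.8546 = 0.1243.
- Within-site variance: 0.24·0.075·0.925 + 0.36·0.115·0.885 + 0.40·0.215·0.785 = 0.1208.
- Ratio: 0.972. With no treatment effect, the pooled standard error is too large by 1/√0.972 − 1 = 1.4%, equal to 2.8% of 500, or about 14 patients.
- With a risk ratio of 7/15 at every site, rates averaged over the arms fall by the factor (1 + 7/15)/2 = 0.733. The between-site part is 0.00346 × 0.733² = 0.00186, against a pooled variance of 0.1066 × 0.8934 = 0.0953. That is 2.0%, so the standard error is 1.0% too large (about 10 patients).

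**Simulation.** There were 400,000 trials per scenario with 120/180/200 patients (two years at the stated volumes). Blocks of 4 and 6 within site were assumed, since the protocol says only that block size varies. One risk ratio was applied at all sites: 0.467 (7/15), and 0.54 (the 46% reduction cited in 9.1). Entries are pooled chi-square / uncorrected CMH, in %.

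| Site rates | Type I error | Power, RR 0.467 | Power, RR 0.54 |
|---|---|---|---|
| Closest, 10/15/18% | 4.89 / 4.97 | 82.6 / 82.8 | 68.0 / 68.3 |
| Low ends, 5/8/18% | 4.56 / 4.95 | 69.8 / 70.4 | 54.8 / 55.7 |
| Midpoints, 7.5/11.5/21.5% | 4.67 / 4.97 | 81.4 / 82.0 | 66.6 / 67.5 |
| High ends, 10/15/25% | 4.71 / 5.00 | 89.4 / 89.8 | 76.8 / 77.4 |
| Furthest, 5/8/25% | 4.26 / 5.00 | 80.4 / 81.8 | 65.3 / 67.3 |

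The gain is 0.2 to 0.3 point with close sites, 0.4 to 0.9 at low, middle or high rates, and 1.4 to 2.0 at the widest spread. If the low-end rates are rescaled to average 15%, a separate simulation gives a gain of 0.95 point at RR 0.467 and 1.4 points at RR 0.54.

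**Confidence interval.** At midpoints and RR 0.467, the mean 95% interval for the risk difference is 10.70 points wide pooled and 10.61 stratified. With no effect, coverage is 95.2% and 95.0%.

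**Interim.** With 250 patients at midpoints, the chance of p < 0.001 is 0.07% v 0.08% with no effect and 8.1% v 8.6% at RR 0.467.

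**Continuity correction.** A corrected CMH at midpoints has type I error 3.7% and power 77.7% (RR 0.467) or 62.0% (RR 0.54), worse than the pooled test.

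**The case against.** The strongest reply is that the gain is trivial. The pooled test is valid, it is the test the sample size was computed for, and at RR 0.467 the two tests reach different decisions in only about 0.3% of simulated trials with close sites and 0.7% at midpoints. All of that stands, and it limits how much weight the point deserves.

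Other parts also stand:
- The closest-site mix reproduces the plan's 15% mean exactly ((60·10 + 90·15 + 100·18)/250 = 15.0%) and shows the smallest gain. Other mixes within the ranges can also average 15%.
- The audit figures are for dehiscence at sites 1 and 3 and infection at site 2, so the contrast between sites for the composite is uncertain.
- The plan specifies no confidence interval, so the width comparison concerns an interval it would need to add.
- Section 5.5 assigns a wound assessor to each site but allows an alternative site for the Day 30 and 90 photographs, so assessment is not wholly tied to site.
- Section 11.2 requires ethics committee review of amendments, and 9.3 fixes the software as SPSS version 20. Whether it produces the uncorrected statistic and the proposed interval has not been checked here.
- A careless implementation with the continuity correction would lose 81.4 − 77.7 = 3.7 points at midpoints, about six times the gain.

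None of this makes the pooled test preferable. In every scenario examined, the uncorrected stratified test had at least as much power and held its type I error at about 5%.

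**Conclusion.** The concern holds and is minor. The primary analysis omits the randomisation stratum although the plan expects large differences in risk between sites. The pooled test's true size is about 4.6% to 4.9% for most readings of the site ranges and 4.3% at the widest spread. The power given up is usually below 1 point. It goes beyond that only with a wider spread, or with a weaker effect combined with a strong site contrast.

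On the plan's 15% v 7% inputs, power stays above 80% with either test. The roughly 70% at low-end site rates reflects the lower event rate, not the choice of test.

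These figures assume enrolment in proportion to transplant volume, one risk ratio at all sites, blocks of 4 and 6, and that the site ranges describe the composite outcome.

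**What to change.** In the synopsis and 9.3, name one primary analysis: a two-sided CMH test stratified by the three sites, stated explicitly to be without continuity correction. Report the Mantel-Haenszel risk difference, with weights n1k·n0k/Nk for site k, and a 95% confidence interval from the Sato variance. Take the number needed to treat as its reciprocal, giving limits only if the interval excludes zero, and use the same estimator for each specific complication. In 9.4, apply the same test at the interim against p = 0.001. Keep the pooled chi-square as a supportive analysis. The sample size need not change.

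The cost is an amendment to those three places, submitted to the ethics committee and in force before the 1-year interim look, plus a check that the named software gives these quantities (otherwise name another program). Site is already recorded as the stratum, so no data or patients are added.

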3.2 Secondary Objectives

Secondary objectives of this study include identification of risk factors for wound complications at the surgical site, as well as reoperation, prolonged hospital stay, allograft survival, delayed graft function. This study will also assess pain, scar healing and quality of life in each treatment arm, and aim to complete a cost-benefit analysis of the Prevena device in renal transplantation.

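### Stepwise selection will not prevent overfitting in the risk-factor model with about 55 events: it inflates the odds ratios of selected factors and, unless the undefined multiplicity adjustment covers all candidates, will often yield false ones

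*Combined protocol and SAP*

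**What the plan says.** Section 3.2 sets the aim: "Secondary objectives of this study include identification of risk factors for wound complications at the surgical site". The synopsis and section 9.3 give the method: "identification of risk factors for wound complications will be assessed by multiple logistic regression of collected variables", with the odds ratio of each variable as the quantity of interest. Section 9.3 then adds: "To prevent overfitting with the selected sample size, variables will be stepwise selected and also assessed for multicollinearity". The same sentence goes on to promise that significance levels will be adjusted for multiplicity. It names no method and attaches the adjustment to the dependent variables, although this model has only one. The paragraph closes by setting p<0.05 for secondary outcomes, of which it has just called this one.

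The statistical sections give no number of candidates, no direction of selection, no entry or removal threshold, no shrinkage and no internal validation. Appendix C, which holds the data-collection items, is not in the text available here, so no variable list is treated as missing. A list of data to collect would in any case differ from a list of pre-specified predictors.

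**The concern.** The plan gives a reason for stepwise selection that the method does not satisfy. Choosing variables by their p-values in the same data that supply the estimates keeps a factor mainly when chance has pushed its estimate away from the null. The odds ratios that survive are therefore biased upward, most of all for weak and moderate factors. The ordinary intervals and p-values take no account of the search.

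Section 9.3 says the purpose is to assess odds ratios, so the bias falls on the quantity the analysis is meant to deliver. If the significance level is not corrected over all candidates, noise variables may also be published as risk factors for wound complications after renal transplant.

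**Working it through.** **Inputs from section 9.1.** "Estimated mean wound complication rate in control arm across 3 sites : 15" (per cent); "Estimated complication rate for Prevena arm (intervention) = 7" (per cent); two-sided alpha 0.05; power 80%; 250 per arm planned.

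**1. The plan's own figure.** With a mean proportion of 0.11:

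{1.96 × √(0.11 × 0.89 × 2) + 0.84 × √(0.15 × 0.85 + 0.07 × 0.93)}² / 0.08² = (0.867 + 0.369)² / 0.0064 = 238.7, so 239 per group. The stated figure is reproduced.

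**2. Expected events.** 250 × 0.15 + 250 × 0.07 = 37.5 + 17.5 = **55**.

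For a range, weight the site ranges in section 9.1 by annual volume:
- Low: (60 × 5 + 90 × 8 + 100 × 18) / 250 = 11.3%.
- High: (60 × 10 + 90 × 15 + 100 × 25) / 250 = 17.8%.

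With the same 7/15 ratio between arms, events are 250 × rate × (1 + 7/15), or 41 to 65. With no treatment effect at 15% they are 500 × 0.15 = 75.

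**3. Events per candidate.** The number of candidates is an assumption. Sections 2.1 and 4.2 name enough recipient, donor and operative items to make 20 or more plausible; 10 to 30 is used here. 55/10 = 5.5, 55/20 = 2.75, 55/30 = 1.8.

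**4. False factors, simple check.** For k independent null candidates each tested at 0.05, the chance of at least one false finding is 1 − 0.95^k: 40%, 64% and 79% for k = 10, 20 and 30.

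**5. Simulation.** 500 patients, 11% event rate, binary covariates with 30% prevalence, forward stepwise logistic regression with entry at p<0.05 and removal at p>0.10, 400 replicates per setting. Prevalence, thresholds and true odds ratios are assumptions, not taken from the plan.

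| Noise candidates only | 10 | 20 | 30 |
|---|---|---|---|
| At least one false factor, unadjusted 0.05 | 40% | 66% | 77% |
| Same, requiring p<0.05/k as well | 4% | 3% | 3% |

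A second set of runs gave 37%, 66% and 76% unadjusted.

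| 20 candidates, three true factors | OR 1.5 | OR 2 | OR 3 |
|---|---|---|---|
| Mean OR when selected, entry 0.05 | 2.24 | 2.44 | 3.20 |
| Share of trials selecting it | 29% | 65% | 98% |
| Mean OR when selected, entry 0.05/20 | 2.80 | 2.96 | 3.41 |

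The second set gave about 2.1 and 2.3 for the two weaker factors at 0.05, and about 2.6 and 2.8 under the stricter rule.

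**6. Readings of the multiplicity clause (20 candidates).**
- No adjustment: a false factor in 59% of trials with three true factors, 66% with none.
- Bonferroni over the selected variables only: 22% and 55%.
- Bonferroni over all candidates: about 3–4%, rising to 7% when candidates are correlated at 0.3. The second set gave 4–7%.

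The last reading controls false factors. It does not remove the inflation in step 5.

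**7. Comparators.** Fitting all 20 candidates gave a false factor in 61% of trials, against 59% for stepwise. Optimism in the AUC was 0.107 for the full fit and 0.037 for stepwise. A pre-specified five-parameter model gave mean odds ratios of 1.50, 2.03 and 3.08 for true 1.5, 2 and 3, with a false factor in 8% of trials (2% with Bonferroni). A pre-specified eight-parameter model gave 1.49, 2.02 and 3.08.

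**The case against.** The strongest reply is that stepwise selection does reduce overfitting compared with entering every collected variable: step 7 shows about a third of the AUC optimism and a similar false-factor rate. That stands. A reader might infer that stepwise selection is what causes the overfitting here. The documents do not support that. The cause is the number of candidates against about 55 events, and stepwise selection leaves it unsolved while adding its own bias.

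A second reply is that the sentence promises a multiplicity adjustment. Section 4.6 refers to an appendix list of dependent variables, so the phrase may well be loose wording for the collected variables, that is, the candidates. On that reading false factors are largely controlled, and the 40%, 66% and 76% figures do not apply. This too stands as a possible reading. But the plan neither names the method nor fixes the scope, the closing p<0.05 pulls the other way, and the upward bias remains on any reading.

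Third, the sizes depend on assumed candidate counts and effects, and all-noise data are a worst case. Section 2.1 cites strong associations with BMI (relative risks of 3.13 and 4.85). For a true odds ratio of 3 the inflation is minor (3.20). The harm is mainly to weak and moderate factors.

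Finally, a reader might take risk-factor identification to be the highest-ranked secondary objective because section 3.2 lists it first. The documents do not rank these objectives, and section 4.6 leaves it out of the secondary outcomes.

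**Conclusion.** The claim that stepwise selection will prevent overfitting is wrong and should be removed. With about 55 events (41 to 75 across the planning ranges) and 20 assumed candidates, true odds ratios of 1.5 and 2 would be reported, when selected, at about 2.1–2.2 and 2.3–2.4, and higher with a stricter entry level. False risk factors are likely at an unadjusted 0.05 and uncommon (about 3–7%) if the correction covers every candidate; the plan does not say which applies. It would go too far to say that the plan ignores multiplicity, or that it will certainly report noise as risk factors. The figures rest on the assumed candidate count, covariate prevalence, thresholds and true effects; the direction of the bias in selected odds ratios does not depend on their exact values. The primary chi-square comparison and the estimated treatment effect are untouched.

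**What to change.** Replace stepwise selection in section 9.3 with one logistic model whose predictors are fixed before outcome data are seen, in practice before the one-year interim analysis in section 9.4.

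- **Predictors.** A short list from section 2.1, for example BMI, diabetes, age and dialysis type, with arm and site always included. Arm takes one parameter, three sites take two, and four predictors take four or five depending on how dialysis is coded. That is 7 or 8 parameters, or 55/7 = 7.9 to 55/8 = 6.9 events each. Immunosuppression follows site practice (section 4.2) and may be hard to separate from site.
- **Fit.** Keep all predictors in the model. Because about 7 events per parameter is low, Firth or ridge shrinkage is a reasonable alternative to the ordinary full fit. Do not use lasso with ordinary intervals, since it also selects on the same data.
- **Multiplicity.** Name the method and state that it applies to all predictors in the model. Without it, five null predictors alone give a false finding in 1 − 0.95^5 = 23% of trials.
- **Reporting.** Give all odds ratios with intervals, report bootstrap-assessed optimism, and label the analysis exploratory.

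The cost is SAP wording and agreement on a list. Fewer variables can be examined, and a penalised fit may need software other than SPSS 20. No change to sample size or data collection is needed.
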